8.3.3 Follow-up of AEs and SAEs

After the initial AE/SAE report, the investigator is required to proactively follow each subject at subsequent visits/contacts. All SAE/non-serious AEs will be followed until resolution, stabilization, the event is otherwise explained, or the subject is lost to follow-up.

Any AEs that are unresolved at the subject's last AE assessment visit in the study are followed up by the investigator for as long as medically indicated, but without further recording in the CRF. AstraZeneca retains the right to request additional information for any subject with ongoing AE(s)/SAE(s) at the end of the study, if judged necessary.

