8.3.2 Time period and frequency for collecting AE and SAE information

AEs and SAEs will be collected from time of signature of informed consent form until 30 days after the last dose of study treatment or the start of new anticancer therapy (whichever comes first). After this period, investigators should report SAEs or other AEs of concern that are believed to be related to prior treatment with study treatment.

All SAEs that occur during the reporting period should be followed to resolution or until the investigator assesses the subject as stable, or until the subject is lost to follow up or withdraws

consent. Resolution/stable means the subject has returned to baseline state of health or the investigator does not expect any further improvement or worsening of the event.

All SAEs/AESIs will be recorded and reported to the sponsor or designee within 24 hours. The investigator will submit any updated SAE/AESI data to the sponsor within 24 hours of it being available.

Investigators are not obligated to actively seek AE or SAE in former study subjects. However, if the investigator learns of any SAE, including a death, at any time after a subject's last visit and he/she considers the event to be reasonably related to the study treatment or study participation, the investigator may notify the sponsor.

The method of recording, evaluating, and assessing causality of AE and SAE and the procedures for completing and transmitting SAE reports are provided in [Appendix B](#).

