8.3.12 Handling of deaths

All deaths that occur during the study, or within the protocol-defined follow-up period after the administration of the last dose of investigational product, should be reported as follows:

- Death, which is unequivocally due to disease progression, should be communicated to the study monitor at the next monitoring visit and should be documented in the eCRF module, but should not be reported as a SAE during the study
- Where death is not due (or not clearly due) to disease progression of the disease under study, the AE causing the death should be reported to the study monitor as an SAE within 24 hours. The report should contain a comment regarding the co-involvement of progression of disease, if appropriate, and should assign a single primary cause of death together with any contributory causes
- Deaths with an unknown cause should always be reported as a SAE but every effort should be made to establish a cause of death. A post-mortem may be helpful in the assessment of the cause of death, and if performed a copy of the post-mortem results (with translation of important parts into English) should be reported in an expedited fashion to an AstraZeneca representative within the usual timeframes.

Deaths occurring after the protocol-defined reporting period (30 days after the last dose of study treatment) should be documented in the Death page. If the death occurred as a result of an event that started after the defined follow-up period and the event is considered to be due to a late-onset toxicity to study treatment, then it should also be reported as an SAE.

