8.4 Safety reporting and medical management

8.4.1 Reporting of serious adverse events

All SAEs have to be reported, whether or not considered causally related to the investigational product, or to the study procedure(s). All SAEs will be recorded in the CRF.

If any SAE occurs in the course of the study, then Investigators or other site personnel inform the appropriate AstraZeneca representatives within one day i.e., immediately but **no later than 24 hours** of when he or she becomes aware of it.

The designated AstraZeneca representative works with the Investigator to ensure that all the necessary information is provided to the AstraZeneca Patient Safety data entry site **within 1**

calendar day of initial receipt for fatal and life-threatening events **and within 5 calendar days** of initial receipt for all other SAEs.

For fatal or life-threatening adverse events where important or relevant information is missing, active follow-up is undertaken immediately. Investigators or other site personnel inform AstraZeneca representatives of any follow-up information on a previously reported SAE within one calendar day i.e., immediately but **no later than 24 hours** of when he or she becomes aware of it.

Once the Investigators or other site personnel indicate an AE is serious in the EDC system, an automated email alert is sent to the designated AstraZeneca representative.

If the EDC system is not available, then the Investigator or other study site staff reports a SAE to the appropriate AstraZeneca representative by telephone.

The AstraZeneca representative will advise the Investigator/study site staff how to proceed.

For further guidance on the definition of a SAE, see [Appendix B](#) of the Clinical Study Protocol.

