Appendix B Adverse event definitions and additional safety information

B 1 Definition of adverse events

An adverse event is the development of any untoward medical occurrence (other than progression of the malignancy under evaluation) in a subject or clinical study subject administered a medicinal product and which does not necessarily have a causal relationship with this treatment. An AE can therefore be any unfavorable and unintended sign (e.g. An abnormal laboratory finding), symptom (for example nausea, chest pain), or disease temporally associated with the use of a medicinal product, whether or not considered related to the medicinal product.

The term AE is used to include both serious and non-serious AEs and can include a deterioration of a pre-existing medical occurrence. An AE may occur at any time, including run-in or washout periods, even if no Study treatment has been administered.

B 2 Definitions of serious adverse event

A serious adverse event is an AE occurring during any study phase (i.e., run-in, treatment, washout, follow-up), that fulfils one or more of the following criteria:

- Results in death
- Is immediately life-threatening
- Requires in-subject hospitalization or prolongation of existing hospitalization
- Results in persistent or significant disability or incapacity.
- Is a congenital anomaly or birth defect
- Is an important medical event that may jeopardize the subject or may require medical treatment to prevent one of the outcomes listed above.

B 3 Life threatening

‘Life-threatening’ means that the subject was at immediate risk of death from the AE as it occurred or it is suspected that use or continued use of the product would result in the subject’s death. ‘Life-threatening’ does not mean that had an AE occurred in a more severe form it might have caused death (e.g., hepatitis that resolved without hepatic failure).

B 4 Hospitalization

Outpatient treatment in an emergency room is not in itself a serious AE, although the reasons for it may be (e.g., bronchospasm, laryngeal oedema). Hospital admissions and/or surgical operations planned before or during a study are not considered AEs if the illness or disease existed before the subject was enrolled in the study, provided that it did not deteriorate in an unexpected way during the study.

B 5 Important medical event or medical treatment

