4.2.3.3.8. Deaths

All deaths and deaths on-treatment or within 30 days of last dose will be summarized. Details of any deaths will be listed for all patients.

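### Protocol 8.3.3 stops CRF recording of any AE unresolved at the last AE visit, with no exception for SAEs; this contradicts 8.3.2 and 8.4.1 and can leave a late fatal outcome out of the fatal-TEAE tables

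*Protocol*

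**What the plan says.** Protocol 8.3.3 covers follow-up of both AEs and SAEs. It opens with a general rule: "All SAE/non-serious AEs will be followed until resolution, stabilization, the event is otherwise explained, or the subject is lost to follow-up". It then says that AEs unresolved at the last AE assessment visit are "followed up by the investigator for as long as medically indicated, but without further recording in the CRF", and that the sponsor may ask for more on events ongoing at the end of the study. No exception is made for serious or fatal events. Appendix B 1 defines the term broadly: "The term AE is used to include both serious and non-serious AEs".

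Three other protocol sections bear on the same events:

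- **8.3.2** sets the window: "AEs and SAEs will be collected from time of signature of informed consent form until 30 days after the last dose of study treatment", or until new anticancer therapy if that is earlier. It adds "All SAEs that occur during the reporting period should be followed to resolution or until the investigator assesses the subject as stable", and requires updated SAE data to reach the sponsor within 24 hours, with no end date.
- **8.4.1** says "All SAEs will be recorded in the CRF", makes the electronic data capture system the normal reporting route, and wants follow-up information on a reported SAE within one calendar day.
- **8.3.12** sends deaths after the 30-day window to the Death page. Its added SAE rule begins "If the death occurred as a result of an event that started after the defined follow-up period" and applies where late-onset toxicity is suspected.

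On the analysis side, SAP 4.2.3.3 and 4.2.3.3.5 tabulate TEAEs leading to death and the drug-related subset. SAP 4.2.3.3.8 is a separate output: "All deaths and deaths on-treatment or within 30 days of last dose will be summarized".

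**The concern.** The issue is the later outcome of events that began inside the collection window. If recording stops at the last AE visit, the AE record keeps the outcome and seriousness it had on that day. A subject may stop drug with an unresolved AE, pass the safety visit at day 30 to 37 and then die of that AE. That subject would have a Death page entry and an AE record with a non-fatal outcome.

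The fatal-TEAE tables are summaries of AEs, and the SAP text gives no rule that links the Death page to the AE record. Such a death could therefore be counted among all deaths and be absent from both fatal-TEAE tables. The clinical database could also disagree with the sponsor's safety database, which receives SAE updates under 8.3.2 and 8.4.1. Any error from this source runs in one direction: it can only lower the fatal-TEAE count.

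**Working it through.** The plan states no figure on this point, so the check is a cross-reading of the sections, followed by simple scaling.

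**Step 1: is the event a TEAE?** SAP 3.2.2.1 classes an AE as treatment-emergent if it occurs or worsens between first dose and 30 days after last dose, or new anticancer therapy if earlier. An event with onset on treatment is a TEAE whatever happens to it later. A fatal outcome is then an attribute of an event already counted. SAP 4.2.3.3.5 sets no limit on the date of death.

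**Step 2: which fields stop being updated?** Protocol 8.3.4 collects outcome, seriousness and grade changes for each AE, and cause and date of death for SAEs. Read literally, 8.3.3 stops updates to all of these after the last AE visit.

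**Step 3: do other sections keep the record open?** Take an AE with onset inside the window, ongoing at the last AE visit and fatal afterwards:

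| Status at last AE visit | 8.3.3 | 8.3.2 and 8.4.1 | 8.3.12 |
|---|---|---|---|
| Already serious | No further CRF recording | Followed to resolution or stability; updates to sponsor; SAEs recorded in CRF | Death page; late-onset SAE rule does not apply |
| Non-serious, later judged related | No further CRF recording | 8.3.2 asks for a report of related SAEs after the window | As above |
| Non-serious, later judged unrelated | No further CRF recording | No clear requirement after the window | As above; the bullet on deaths during the study may apply |

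Row 1 is a direct contradiction. In row 2 a report is requested, but nothing says that the existing AE record is updated. Row 3 is the clearest gap: the Death page is required, but no sentence clearly requires the AE record to change, and 8.3.3 says it does not.

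**Step 4: scale.** The planned sizes are 12 (Phase 1), 33 (Cohort A) and 60 (Cohort B), from protocol 9.2. One missed event changes the reported incidence by 1/n:

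- Cohort B: 1/60 = 1.7 percentage points.
- MCL group: 1/33 = 3.0 points at most. SAP 4.1 pools Phase 1 MCL subjects with Cohort A, which enlarges the denominator.
- Phase 1, a reporting group of its own in SAP 4.1: 1/12 = 8.3 points.

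The documents give no rate for such events. If 0 to 2 cases are assumed, the range is 0 to 3.3 points in Cohort B (2/60) and 0 to 6.1 points in the MCL group before pooling (2/33).

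**The case against.** The strongest reply is that the protocol already covers serious events. Section 8.3.2 keeps SAEs under follow-up with no end date for updates, 8.4.1 places all SAEs in the CRF, and 8.3.4 lists cause and date of death among the SAE variables. A site that reads these as the specific rule and 8.3.3 as the general one would update the record. This stands to the extent that a reader should not infer that an ongoing SAE necessarily keeps its old outcome. But nothing says which rule prevails, and the follow-up provisions send updates to the sponsor without saying that the AE record in the CRF is revised.

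Second, 8.3.12 also says that, for deaths during the study not clearly due to progression, the causal AE is reported as an SAE within 24 hours. A subject in disease or survival follow-up could be regarded as still in the study. That reading is reasonable and narrows the gap. It does not close it, because the later paragraph treats deaths after the window separately and does not mention an AE that began inside it.

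Third, the deaths are not hidden. They go to the Death page, to the all-deaths summary and to a listing, and protocol 7.2 re-checks the survival status of the safety set at final analysis. This stands in full. What can be lost is the attribution of a death to a TEAE.

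Fourth, a reader might infer that later non-fatal worsening of grade is lost in the same way. The documents do not support that as a consequence of 8.3.3: worsening more than 30 days after last dose falls outside the SAP's treatment-emergent window in any case.

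Finally, safety is descriptive and no case count is given. That is also true, and it limits the point to accuracy of reporting.

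**Conclusion.** The point holds as a contradiction between sections with a possible reporting consequence. Section 8.3.3 ends CRF recording for any unresolved AE, 8.3.2 and 8.4.1 require continued handling of SAEs, and the late-death paragraph of 8.3.12 omits events that began inside the window. Where a site applies 8.3.3 literally, a TEAE that turns fatal after the last AE visit can be missing from the fatal-TEAE table and, if related, from the drug-related one. The most exposed case is an AE that is non-serious at the last visit, later fatal and judged unrelated.

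Per case the effect is 1.7 points in Cohort B, at most 3.0 in the MCL group and 8.3 in Phase 1. These figures assume the planned enrolment and one missed event; how many will occur cannot be told from the documents. The conclusion also assumes that the fatal-TEAE tables are built from the AE record without reconciliation to the Death page, on which the SAP text is silent. A reader might infer a demonstrated bias towards better safety. The documents support only a possible undercount, which depends on how sites resolve the conflict.

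**What to change.** Reconcile the passages:

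1. **Protocol 8.3.3:** limit the end of CRF recording to AEs that stay non-serious. For SAEs, and for AEs with onset in the window that later become serious or fatal, keep updating outcome, seriousness and the relevant dates in the CRF until resolution, stabilization or the cohort's final data cut-off. That end point fits protocol 4.4, which stops data collection other than paper SAE reports after the final cut-off.
2. **Protocol 8.3.12:** add that a death after the window caused by an AE that began within it is entered as the fatal outcome of that AE.
3. **SAP 4.2.3.3.5:** state that fatal TEAEs are counted by AE onset, whatever the date of death, and are reconciled with the Death page.

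The cost is wording in two protocol sections, a sentence in the SAP, and a few more CRF updates on events that sites already follow. No visits are added. The reported fatal-TEAE rate may come out slightly higher.

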8.3.4 Adverse event data collection

The following variables will be collected for each AE;

- AE (verbatim)
- The date when the AE started and stopped
- CTCAE grade (version 5.0)/changes in CTCAE grade
- Whether the AE is serious or not
- Investigator causality rating against the Investigational Product(s) (Yes or No)
- Action taken with regard to Investigational Product(s)
- Whether the AE caused subject's withdrawal from study (Yes or No)
- Outcome
- Administration of treatment for the AE

In addition, the following variables will be collected for SAEs:

- Date AE met criteria for serious AE

- Date investigator became aware of serious AE
- AE is serious due to
- Date of hospitalization
- Date of discharge
- Probable cause of death
- Date of death
- Autopsy performed
- Causality assessment in relation to study procedure(s)
- Causality assessment to other medication
- Description of the SAE

8.3.5 Causality collection

The Investigator will assess causal relationship between Investigational Medicinal Product and each AE and/or incident, and answer ‘yes’ or ‘no’ to the question ‘Do you consider that there is a reasonable possibility that the event may have been caused by the IMP?’

For SAEs and serious incident, causal relationship should be assessed for other medication and study procedures. Note that for SAEs that could be associated with any study procedure the causal relationship is implied as ‘yes’.

A guide to the interpretation of the causality question is found in Appendix [B7](#) to the Clinical Study Protocol.

8.3.6 Adverse events based on signs and symptoms

All AEs spontaneously reported by the subject or care provider or reported in response to the open question from the study site staff: ‘Have you had any health problems since the previous visit/you were last asked?’, or revealed by observation will be collected and recorded in the CRF. When collecting AEs, the recording of diagnoses is preferred (when possible) to recording a list of signs and symptoms. However, if a diagnosis is known and there are other signs or symptoms that are not generally part of the diagnosis, the diagnosis and each sign or symptom will be recorded separately.

8.3.7 Adverse events based on examinations and tests

The results from the Clinical Study Protocol mandated laboratory tests, vital signs, ECGs and other safety assessment will be summarized in the CSR. Deterioration as compared to baseline in these parameters will therefore only be reported as AEs if they fulfil any of the SAE criteria or are the reason for discontinuation of treatment with the investigational product.

If deterioration in a laboratory value, vital sign, ECG or other safety assessment is associated with clinical signs and symptoms, the sign or symptom will be reported as an AE and the associated laboratory result/vital sign will be considered as additional information. Wherever possible the reporting Investigator uses the clinical, rather than the laboratory term (e.g., anemia versus low hemoglobin value). In the absence of clinical signs or symptoms, clinically relevant deteriorations in non-mandated parameters should be reported as AE(s).

Deterioration of a laboratory value, which is unequivocally due to disease progression, should not be reported as an AE/SAE.

Any new or aggravated clinically relevant abnormal medical finding at a physical examination as compared with the baseline assessment will be reported as an AE unless unequivocally related to the disease progression.

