6.6 Dose delay and dose modification

6.6.1 Dose delay

Treatment with acalabrutinib should be held for any unmanageable, potentially study drug-related toxicity that is Grade ≥ 3 in severity. Any other clinically important events where dose delays may be considered appropriate by the investigator must be discussed with the sponsor. Study drug may be held for a maximum of 28 consecutive days from expected dose. Study treatment should be discontinued in the event of a toxicity requiring the postponement of dosing lasting >28 days, unless reviewed and approved by the sponsor.

Note: temporary withholding of study drug for as little as 7 days can cause a transient worsening of disease and/or of constitutional symptoms. Refer to Section 7.1 for more information on assessing disease progression under these circumstances.

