6.6.2 Dose modification

The actions in Table 7 should be taken for the following toxicities (according to CTCAE criteria version 5.0 or higher):

- Grade 4 neutropenia (ANC $< 500/\mu\text{L}$) for > 7 days (Myeloid growth factors are permitted per Consensus of Chinese Experts ([Version 2015](#)) and use must be recorded on the eCRF).

- Grade 3 platelets decreases in the presence of clinically significant bleeding
- Grade 4 platelets decreases
- Grade 3 or 4 nausea, vomiting, or diarrhea, if persistent despite optimal antiemetic and/or anti-diarrheal therapy
- Any other Grade 4 toxicity or unmanageable Grade 3 toxicity.

If the toxicity resolves or reverts to \leq CTCAE grade 1 or baseline within 28 days of onset and the subject is showing clinical benefit, treatment with acalabrutinib may be restarted using the rules below for dose modifications (see [Table 7](#)). Whenever possible, any dose adjustment of acalabrutinib should be discussed between the investigator and the sponsor before implementation. The appropriate clinic staff should dispense the study drug for the new dose level and instruct the subject/caregiver about the change in dose level. Any changes to the dosing regimen must be recorded in the appropriate eCRF.

In case a dose reduction is necessary, the study intervention will be administered as follows.

Dose modification guidelines for study intervention-related toxicities are provided below. Appropriate and optimal treatment of the toxicity is assumed prior to considering dose modifications. Prior to discontinuation of study intervention due to toxicities, please consult with the study physician.

Table 7 Dose modifications for toxicity

Occurrence	Action
1 st -2 nd	Hold acalabrutinib until recovery to Grade \leq 1 or baseline; may restart at original one-day dose level (100 mg BID)
3 rd	For non-hematologic AEs, discontinue acalabrutinib. For thrombocytopenia with significant bleeding, discontinue acalabrutinib. For other hematologic AEs, upon recovery to Grade \leq 1 or baseline, restart at 100 mg QD.
4 th	For hematologic AEs, discontinue acalabrutinib.

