8.1.3 Clinical laboratory assessments

See [Table 10](#) for the list of clinical safety laboratory tests to be performed and to the SoA for the timing and frequency. All protocol-required laboratory assessments, as defined in the table, must be conducted in accordance with the laboratory manual and the SoA.

The Investigator should make an assessment of the available results with regard to clinically relevant abnormalities. The laboratory results should be signed and dated and retained at centre as source data for laboratory variables.

For information on how AEs based on laboratory tests should be recorded and reported, see Section [8.3.7](#).

Additional laboratory samples may be collected if clinically indicated at the discretion of the Investigator. The date, time of collection and results (values, units and reference ranges) will be recorded on the appropriate eCRF.

The clinical chemistry, hematology (see paragraphs below for specific requirements for CLL subjects in phase 2 – cohort B), pregnancy test, coagulation, urinalysis, hepatitis, HIV and serum immunoglobulin levels analyses will be performed locally at the visits as indicated in the SoA (see [Table 1](#), [Table 2](#) and [Table 3](#)), therefore sample volumes may vary according to local practice. If screening assessment clinical chemistry, hematology, coagulation and urinalysis are performed within 5 days prior to the baseline visit (i.e. first dose day: Phase 1 portion- at Cycle 0 Day 1; Phase 2 portion- at Cycle 1 Day 1), they do not need to be repeated at the baseline visit. T/B/NK cell count (i.e., CD3, CD4, CD8, CD19, CD16/56) will be performed at the central laboratory, samples will be collected, labelled, stored, and shipped as detailed in the Laboratory Manual.

All samples will be used up, or disposed of after analyses.

Additional laboratory tests requirement for CLL subjects in phase 2 – cohort B only:

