8.2.3 Vital signs

Vital signs (Blood pressure, pulse rate, and body temperature) should be assessed after at least 5 minutes of rest for the subject in a quiet setting without distractions (e.g., television, cell phones).

Changes from baseline abnormalities should be recorded in subject notes. New or worsened clinically significant abnormalities should be recorded as AEs on the Adverse Event eCRF.

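### Protocol 8.3.7 contradicts 8.2.3 on when a vital-sign change is an AE, and its two recording triggers omit laboratory cytopenias that lead to a hold or dose reduction

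*Protocol*

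**What the plan says.** **Recording rules.** Protocol 8.3.7 covers protocol-mandated laboratory tests, vital signs, ECGs and other safety assessments. Deterioration in these "will therefore only be reported as AEs if they fulfil any of the SAE criteria or are the reason for discontinuation of treatment". If symptoms are present, the symptom is the AE. Its provision for symptom-free deterioration is limited to non-mandated parameters. For vital signs, Protocol 8.2.3 says: "New or worsened clinically significant abnormalities should be recorded as AEs on the Adverse Event eCRF". For laboratory tests, Protocol 8.1.3 sends the reader to 8.3.7: "For information on how AEs based on laboratory tests should be recorded and reported".

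**Dose actions.** Protocol 6.6.2 lists the toxicities that lead to a Table 7 action, among them Grade 4 neutropenia lasting more than 7 days and "Grade 4 platelets decreases". Table 7 calls such events AEs in its third-occurrence row: "For other hematologic AEs, upon recovery to Grade" 1 or baseline, treatment restarts at 100 mg QD. A hold is distinct from discontinuation. Section 6.6.1 says: "Study drug may be held for a maximum of 28 consecutive days from expected dose".

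**General definition.** Appendix B1 says: "An AE can therefore be any unfavorable and unintended sign (e.g. An abnormal laboratory finding".

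**Planned tables.** Protocol 9.4.2 and SAP 4.2.3.3.4 summarize treatment-emergent AEs that led to dose delay, interruption or modification. SAP 3.2.2.1 and 4.2.3.3.7 define and tabulate events of clinical interest (ECIs), which include cytopenias and hypertension.

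**The concern.** For vital signs, two sections of one protocol give opposite instructions for the same finding, so the hypertension ECI count would partly reflect how sites read the protocol.

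For laboratory tests, the recording rule does not match the tables that depend on it. A cytopenia that leads to a hold or reduction is exactly the event that the interruption and modification tables are meant to show. Yet 8.3.7 requires an AE record only if the event is serious or ends treatment. Investigator causality, action taken with study drug and outcome are collected on the AE record (Protocol 8.3.4). Without that record, no planned table links the event to the dose action. Cytopenias are listed among the important identified risks (Protocol 2.3.2.2), so the tables affected are not peripheral.

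**Working it through.** The plan states no figure on this point to reproduce. The main check is to apply each rule to the same case.

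**Step 1: trace of asymptomatic cases that the investigator does not judge serious**

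| Case | Under 8.3.7 | Under other text |
|---|---|---|
| Clinically significant blood-pressure rise, treatment continues | Not an AE | AE (8.2.3) |
| Grade 4 neutropenia >7 days or Grade 4 platelets, 1st or 2nd occurrence: hold | Not an AE | Table 7 and Appendix B1 point to an AE |
| Same, 3rd occurrence: restart at 100 mg QD | Not an AE | As above |
| Same, 4th occurrence: discontinue | AE | Agrees |

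If 8.3.7 is followed, up to three dose-altering occurrences in one subject can pass before an AE record is required. Grade alone does not close the gap, because Appendix B6 separates severity from seriousness.

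**Step 2: limits of the two conflicts**
- Section 8.2.2 (physical examination) carries the same sentence as 8.2.3, but the last paragraph of 8.3.7 agrees with it. Among these sections, the direct contradiction is specific to vital signs.
- Of the five triggers in 6.6.2, two are defined by a laboratory value alone. One is a laboratory value plus bleeding, one is gastrointestinal, and the fifth is "Any other Grade 4 toxicity or unmanageable Grade 3 toxicity", which may or may not be laboratory-only. This shows that the case exists; it says nothing about how often it occurs.
- Appendix B5 gives blood dyscrasias, such as neutropenia or anemia requiring transfusion, as examples of important medical events. Cytopenias judged serious on that basis remain reportable.
- Reductions should be fewer than holds, because Table 7 reduces only at the third occurrence.

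**Step 3: what one unrecorded subject is worth**

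The change in a percentage is 100/n, using planned sizes (Protocol 9.2) and the SAP's presentation groups (SAP 4.1):
- Cohort B, n=60: 100/60 = 1.7 points.
- Combined MCL, n=33 if no Phase 1 subject has MCL: 100/33 = 3.0 points. If all 12 do, n = 33 + 12 = 45 and 100/45 = 2.2 points.
- Phase 1, n=12: 100/12 = 8.3 points.

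This applies to a subject whose only qualifying event goes unrecorded. It is a sensitivity per subject, not an estimate of how many there are.

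**Step 4: what is captured elsewhere**
- Laboratory: CTCAE grades, shift tables and counts of abnormal values (SAP 4.2.3.4).
- Vital signs: listed and summarized (SAP 4.2.3.5).
- Dosing: interruptions and reductions in the eCRF, and reasons for missed doses in the diary (Protocol 6.4).
- Exposure: withholdings count only from 7 consecutive days and reductions from 3 (SAP 3.2.2.2). Shorter holds still lower actual exposure, for each full day without drug, and relative dose intensity (SAP 3.2.2.2, 3.2.2.3). Both are tabulated (SAP 4.2.3.2), with no cause listed.
- Sponsor review of laboratory values, vital signs and ECGs for other significant AEs (Protocol 9.4.1.1).

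None of these creates an AE record with causality and action taken.

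**The case against.** The strongest reply is that 8.3.7 is a deliberate convention. Mandated results are summarized in the report anyway, so they become AEs only when serious or treatment-ending, which avoids double counting. On this view, Appendix B1 says only what an AE can be, and a specific recording rule may narrow it. Section 6.6.2 acts on CTCAE toxicities whether or not an AE is recorded, so the word AEs in Table 7 may be loose wording. Other routes also leave a trace. Section 8.3.6 collects events revealed by observation and prefers diagnoses. Concomitant treatments carry an indication (6.5), and myeloid growth factor use must be entered in the eCRF (6.6.2). The dosing form may capture a reason for interruption, which the documents do not show.

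Much of this stands as a limit on impact. It explains leaving out incidental values. It does not explain the contradiction with 8.2.3, nor why tables of AEs leading to dose change are planned when the rule can leave out the AEs they need.

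Three stronger readings are tempting, and the documents do not support them:
- **That these events will certainly be absent from the AE data.** Table 7 and Appendix B1 may lead sites to record them, so recording is uncertain.
- **That the safety information is lost, or that short holds vanish.** Laboratory grades, vital signs, dosing records, actual exposure and relative dose intensity all remain.
- **That AE rates are materially understated.** No number of affected subjects can be derived, and the 100/n figures and trigger count give no frequency.

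**Conclusion.** The point holds as an inconsistency in recording rules that can leave planned tables incomplete. The vital-sign contradiction is direct. The laboratory gap is conditional: it needs a site that follows 8.3.7 and a cytopenia that is asymptomatic, not judged serious, and met with a hold or reduction but not discontinuation. Such an event is missing from the interruption and modification tables and from the cytopenia ECI table.

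The size is unknown. At planned enrollment, each unrecorded subject is worth 1.7 points in Cohort B and 2.2 to 3.0 points in the combined MCL group. The Phase 1 figure of 8.3 points may have little practical weight, since the protocol estimated that part would be complete in Q2 2022.

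Safety is reported descriptively (Protocol 1.2), and no effect on the primary endpoint or on a dose decision is shown. The point merits correction because the change is specific and cheap, not because a safety signal would otherwise be hidden.

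**What to change.** 1. Reconcile Protocol 8.2.3 and 8.3.7 to a single AE-recording rule for vital signs.
2. Add a third recording trigger to 8.3.7: the deterioration leads to interruption or reduction of study drug. State that it includes laboratory tests, so that 8.3.7 agrees with Table 7 and the planned tables.
3. Before each remaining data cut-off, reconcile eCRF interruption and reduction records against the AE log. Include holds under 7 days and use the diary reasons for missed doses.
4. In the CSR, state that cytopenias without a dose action still follow the 8.3.7 convention, and refer to the CTCAE-graded laboratory tables for cytopenia incidence. Note any change in recording before and after the amendment.

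Items 2 and 3 repair the interruption and modification tables and the capture of dose-altering cytopenias. They do not make cytopenia ECI counts consistent in general, which is why item 4 is needed. No dose or clinical rule changes.

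The cost is a wording amendment plus reconciliation. Five cut-offs are planned (2 for Phase 1 and Cohort A, 3 for Cohort B), so at most five rounds, fewer if some have passed. Reported AE counts would be somewhat higher. A late change brings some before-and-after difference in recording, which the reconciliation reduces but may not remove.
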